4. The following laboratory results should be collected: Hb, leukocytes, lymphocytes, neutrophils, platelets, sodium (Na), potassium (K), creatinine, glucose, total bilirubin, INR, ALT, AST, amylase, LDH, D-dimer, CRP, procalcitonin, ferritin. Repeat at baseline if >24 h since screening. If not, enter laboratory results from screening. If ferritin and procalcitonin are not routinely gathered at a site for clinical follow-up, these analyses should be prioritized at baseline, D8 and D15.

5. If still hospitalized. At discharge or early discontinuation, register WHO disease progression scale, review concomitant medication and adverse events as detailed in section 8.
6. Specify oxygen therapy: a) Nasal prongs, b) Face mask, c) Face mask with reservoir, d) High flow oxygen e) Non-invasive ventilation (NIV) f) Mechanical ventilation/Extracorporeal membrane oxygenation (ECMO) Enter numbers of litres of O₂ provided or fraction of inspired O₂ (FiO₂), unless on ECMO
7. Review WHO stage including mode of oxygen therapy for end point assessment (progression on WHO scale)
8. If discharged, endpoint assessments including sustained recovery, will be conducted by telephone contact with the patient and/or by reviewing patient records and/or contacting primary caretaker and/or relatives.

2. Introduction

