7.2. Participant Discontinuation/Withdrawal from the Study

A participant may withdraw from the study at any time at his/her own request or may be withdrawn at any time at the discretion of the investigator for safety, behavioural, or compliance reasons. This is expected to be uncommon.

At the time of discontinuing from the study, if possible, an early discontinuation visit should be conducted. See section 8. for data to be collected at the time of study discontinuation and follow-up and for any further evaluations that need to be completed.

The participant will be permanently discontinued from the study intervention and the study at that time.

If the participant withdraws consent for disclosure of future information, the sponsor may retain and continue to use any data collected before such a withdrawal of consent.

If a participant withdraws from the study, he/she may request destruction of any samples taken and not tested, and the investigator must document this in the study site records.

There will be no replacements of withdrawn patients.

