7.3. Lost to Follow-Up

Lost to follow-up should not occur during the hospitalization period. However, after discharge from the hospital, participants could be lost to follow-up.

A participant will be considered lost to follow-up if he/she is unreachable for the study site per telephone directly to the patient or relatives (for at least two days), or by written correspondence, after hospital discharge and until end of study.

8. Study Assessments and Procedures

General instructions

Study procedures and their timing are summarized in Schedule of Assessments (SoA, section 1.2). Protocol waivers or exemptions are not allowed.

Safety concerns should be discussed with the sponsor or sponsor representative immediately upon notice, to determine if the participant should continue or discontinue the study intervention.

Adherence to the study design requirements, including those specified in the SoA, is essential and required for good study conduct.

- All assessments in level I (blue background colour in SoA table) are mandatory.
- Level II assessments (green background colour) include biobanking (necessary for virological outcomes) and are encouraged whenever possible.
- Level III assessments (grey background colour) include add-on studies on extended biobanking, imaging organ function and PROM. The accurate and complete description of what is to be measured and monitored will be defined by the units that run level III. This level will form the basis of sub-studies and is optional but should be performed according to common standardised protocols and standard operating procedures.

Screening assessments:

Screening for inclusion should be performed as soon as possible after hospitalisation. For participants progressing in Part A, screening for Part B should be done as soon as possible after progression. All screening evaluations must be completed and reviewed to confirm that potential participants meet all eligibility criteria. The investigator will maintain a screening log to record details of all participants screened and to confirm eligibility or record reasons for screening failure, as applicable.

Procedures conducted as part of the participant's routine clinical management (e.g., blood count) and obtained before signing of the informed consent form may be utilized for screening or baseline purposes provided the procedures meet the protocol-specified criteria and are performed the same day as screening or within 24 hours for baseline.

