 - If ferritin and procalcitonin are not routinely gathered at a site for clinical follow-up of the patient, these analyses should be prioritized at baseline, D8 and D15.
- Obtain vital signs including height in cm and weight in kg, see section 8.3.2.
- Collect data on oxygen therapy, see section 8.1.2.
- Register WHO COVID-19 disease progression scale (0-10), see section 8.1.1.
- Details of study treatment administration according to intervention-specific sub-protocol

Assessment until discharge:

Participants will be assessed daily for AE and SAE while hospitalized, see section 8.6.

- Note AE and SAE in the eCRF upon notice
- Safety concerns should be discussed with the sponsor to determine if the participant should continue or discontinue study intervention

The following clinical data will be noted in the eCRF obtained on Days 3, 5, 8 (± 1 day), and thereafter weekly (Day 15 ± 3 , Day 22 ± 3 , Day 29 ± 3 , etc.)

- Obtain vital signs, see section 8.3.2.
- Collect data on oxygen therapy, see section 8.1.2.
- Register WHO COVID-19 disease progression scale (0-10), see section 8.1.1.
- Review concomitant medication and note changes in the eCRF
- Draw and register blood samples for clinical safety laboratory tests (see section 8.3.5.)
 - If ferritin and procalcitonin are not routinely gathered at a site for clinical follow-up of the patient, these analyses should be prioritized at baseline, D8 and D15.

Details of study treatment adherence and administration will be given in the intervention-specific sub-protocol.

For level II of commitment:

Blood samples and naso/oropharyngeal swabs should be obtained at baseline (D1) before drug intervention starts. In addition, blood samples will be obtained on Days 3, 8, 15 and 22 (all ± 1 day), and naso/oropharyngeal swabs on Days 3, 8, 15 (all ± 1 day), as long as the patient is hospitalized.

Day 15 ± 3 , 29 ± 3 , 61 ± 7 :

If the patient has been discharged, the following information is gathered by phone or by reviewing the patient records:

- Alive or dead

If alive, recovery status

- Readmitted to hospital
- If readmitted, date of readmission and reason for readmission. Report as SAE.
- Review concomitant medication
- Adverse events by open-ended and non-leading verbal questioning of the participant

Follow-up assessment at Day 91 ± 14 :

A follow-up assessment by phone will be performed on Day 91 (± 14 days):

- Alive or dead

If alive, recovery status

- Readmitted to hospital

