- If readmitted, date of readmission and reason for readmission. Report as SAE.
- Review concomitant medication
- Adverse events by open-ended and non-leading verbal questioning of the participant
- Check that patient has answered online patient reported outcome measure (the Oslo COVID-19 QLQ-PW80)

Discharge visit/Early discontinuation visit

- Register WHO COVID-19 disease progression scale (0-10), see section 8.1.1.
- Review concomitant medication and adverse events
- If discharged, register whether the patient is discharged to home, home care facilities, other hospitals or other institutions or locations
- If early discontinuation, register reason for early discontinuation
- Participant withdrew consent to further participation
- Participant withdrawn by the investigator for safety, behavioural or compliance reasons including lost to follow-up
- Death
- For early discontinuation, answer online patient reported outcome measure (the Oslo COVID-19 QLQ-PW80).

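### The loss and withdrawal rules (sections 7.2, 7.3 and 8) do not match the vital-status sources in SoA footnote 8, so Day 61 status of an unreachable participant may go uncollected

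*Protocol*

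**What the plan says.** Four parts of the protocol bear on a discharged participant who cannot be reached.

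- **Definition of loss (section 7.3).** The participant is "unreachable for the study site per telephone directly to the patient or relatives (for at least two days), or by written correspondence", with the time span "after hospital discharge and until end of study". Review of records is not part of the test.
- **How loss is filed (section 8, discharge/early discontinuation visit).** One reason to register for early discontinuation is "Participant withdrawn by the investigator for safety, behavioural or compliance reasons including lost to follow-up".
- **Consequence of withdrawal (section 7.2).** The investigator may withdraw a participant for safety, behavioural or compliance reasons; loss to follow-up is not among them. On withdrawal, "The participant will be permanently discontinued from the study intervention and the study at that time".
- **Where vital status may come from.** For Days 15, 29 and 61, section 8 says "If the patient has been discharged, the following information is gathered by phone or by reviewing the patient records", and the first item is whether the participant is alive. Footnote 8 of the Schedule of Assessments says that endpoint assessments after discharge "will be conducted by telephone contact with the patient and/or by reviewing patient records and/or contacting primary caretaker and/or relatives".

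The Part B primary endpoint is death from any cause within 60 days. Section 9.3.2 censors participants without a final outcome when information on them stops. It promises substantial effort to limit losses, and plans sensitivity analyses in which all lost participants, in both arms, are counted as events or all as non-events.

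**The concern.** Whether someone was alive at Day 60 can often be established without speaking to that person. The loss rule nevertheless rests on contact alone, and the filing rule turns an unreachable participant into a withdrawn one. A participant who stops treatment stays in follow-up under section 7.1, whereas one who is merely hard to reach could get less follow-up without having withdrawn consent. Section 8.6.3 also uses the section 7.3 definition to end follow-up of serious adverse events.

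A participant who has died cannot answer the telephone, so loss defined by failed contact is plausibly related to the Part B endpoint, while censoring treats it as unrelated. Deaths after discharge would be missed and observed mortality would be too low. No analysis plan can recover a vital status that sites did not collect, so this belongs in the protocol.

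**Working it through.** **1. Reading the passages together**

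| Question | 7.3 | 8, early discontinuation | 7.2 | 8, Days 15/29/61, and footnote 8 |
|---|---|---|---|---|
| Are records a source? | Not mentioned | Not mentioned | Not mentioned | Yes, as an alternative |
| Is loss a withdrawal? | Not stated | Yes, by the investigator | Not among the reasons | Not stated |
| Does follow-up continue? | Not stated | Filed as early discontinuation | Ends on withdrawal | Assumed to continue |

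The time span in 7.3 can be read in two ways. If it means unreachable all the way to Day 91, loss cannot be an early discontinuation, which is how section 8 files it. If it only marks the period in which loss may be declared, loss can be declared before Day 61. Either way the sections need reconciling.

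**2. The plan's own sample size**

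Inputs (section 9.5.1): 15% versus 10% mortality, two-sided 5%, 90% power, log-rank test, equal allocation.

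- Hazard ratio = ln(0.90)/ln(0.85) = 0.648, as stated.
- Freedman events = 231. Per arm: 231/(0.15 + 0.10) = 924, as stated.
- Allowance for dropout: 950 − 924 = 26 per arm; 26/950 = 2.7%.

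**3. Power if loss is unrelated to outcome**

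The protocol gives no expected loss rate, so 0 to 10% per arm, equal in both arms, is assumed. With 950 randomised per arm and loss l, the worst-case rates are p(1 − l) + l and the best-case rates are p(1 − l). For example, 2.7% loss gives 17.3% versus 12.5% in the worst case.

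| Loss per arm | Log-rank (Freedman), lost removed | Worst case, two proportions | Best case, two proportions |
|---|---|---|---|
| 0% | 90.8% | – | – |
| 2.7% | 90.0% | 84.6% | 90.1% |
| 5% | 89.3% | 79.0% | 89.3% |
| 10% | 87.7% | 66.9% | 87.4% |

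Loss costs little power in the main analysis but weakens the worst-case analysis considerably.

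**4. Attenuation if the lost are deaths**

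Let s be the share of deaths occurring after discharge and q the share of those missed. Neither is in the protocol; both are assumed. If missed deaths count as survivors, observed mortality is p(1 − sq). If they leave the denominator, it is p(1 − sq)/(1 − psq). If only these deaths are lost, a Kaplan-Meier estimate with censoring lies between the two.

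- s = 0.1, q = 0.5: 14.25% versus 9.5%, difference 4.75 points. With the reduced denominator, 14.25/99.25 = 14.36% versus 9.5/99.5 = 9.55%, difference 4.81.
- s = 0.2, q = 0.5: 13.5% versus 9.0%, difference 4.5 points. With the reduced denominator, 13.5/98.5 = 13.71% versus 9.0/99.0 = 9.09%, difference 4.62.

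With missed deaths counted as survivors, the risk ratio stays at 9.5/14.25 = 9.0/13.5 = 0.667. Log-rank power with 950 per arm falls from 90.8% to 89.1% and 87.2% respectively.

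**5. Non-inferiority (default margin of 3 points, section 9.1)**

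Take a true 18% versus 15%, exactly at the margin, with s = 0.2 and q = 0.5. Observed rates are 16.2% versus 13.5%, difference 2.7 points. With the reduced denominator, 16.2/98.2 = 16.50% versus 13.71%, difference 2.79. The error moves the result towards a non-inferiority claim.

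**The case against.** A reader might infer that two days of unanswered calls at Day 15 allow a site to close a participant out and never look for vital status. The documents do not support that. Two days is a minimum, relatives and letters are part of the test, and the sentence in 7.3 runs to the end of the study. Records are expressly a source at Day 61. No passage says that a missed call ends later contacts. The phrase in section 8 sits in a list of reasons to register, which also includes death, and can be read as coding rather than as an instruction to stop.

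A reader might also infer that the treatment comparison is biased between arms because tracing effort differs. Nothing in the protocol shows unequal tracing. The only sub-protocol summarised, the Part B baricitinib trial, is double blind. Open-label comparisons are permitted by the master protocol, so the possibility exists there, but no more than that.

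Section 9.3.2 does plan worst- and best-case analyses, and the illustrated attenuation is small. These points stand and limit the size of the concern. They do not remove it. The record sources are worded as alternatives, so a check after failed calls is allowed but not required. The promise of effort in 9.3.2 has no matching step in 7.3. The two imputations make the same assumption in both arms, so they do not address unequal loss.

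**Conclusion.** The concern holds as a misalignment: sections 7.2, 7.3 and 8 do not fit footnote 8 and the Day 15/29/61 procedure. Followed literally, they can leave Day 61 vital status uncollected for an unreachable participant who has not withdrawn consent, and censoring that participant would be informative for the Part B death endpoint.

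The size is unknown. The attenuation figures rest on assumed shares of deaths after discharge (10 to 20%) and of those missed (half), the same in both arms. On those assumptions the effect is probably minor for superiority. For a non-inferiority comparison it is also modest, but in the direction that favours the claim. This is an improvement worth making because it is cheap and concerns the primary endpoint; it does not show that the trial's result would be wrong.

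**What to change.** - In 7.3, state that a participant is lost for the primary endpoint only if Day 61 vital status is still unknown after all the sources in footnote 8 (participant, relatives, patient records, primary caretaker) have been tried. Registers can be an optional further source where national law allows.
- State that a missed contact is a missed visit and that later scheduled contacts are still attempted.
- In section 8, delete the mention of loss to follow-up from the investigator-withdrawal reason and record loss as its own category.

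The cost is a short amendment, one changed category in the eCRF, and a record look-up for the few participants who cannot be reached. The required sources are ones the protocol already permits.

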1.2. Schedule of Assessments (SoA)

Procedure	Screening	Baseline	Assessments during hospitalisation	Primary endpoint Part A	Core secondary end point	Primary endpoint Part B	End of study/Early withdrawal
Day ± window		1	Day 3, 5, 8 (all ±1 day), then weekly (±3 d), or until discharge	15±3	29±3	61±7	91±14
Screening for eligibility¹							
Review SARS-CoV-2 laboratory results	X						
Informed consent	X						
Allocation to EU-SolidAct Part A or B by WHO disease stage ²	X						
Baseline procedures							
Demographics and medical history	X	X					
Randomization		X					
Standard of care (SoC) ³		X					
Study intervention		X	Note doses given				
Safety laboratory							
Safety biochemistry ⁴	X	(X)	X	X ⁵	X ⁵	X ⁵	X ⁵
Pregnancy test		X					
Study procedures							
Vital signs including SpO ₂		X	X	X ⁵	X ⁵	X ⁵	X ⁵
Review oxygen therapy ⁶		X	X	X ⁵	X ⁵	X ⁵	X ⁵
Review WHO stage ⁷		X	X	X ⁵	X ⁵	X ⁵	X ⁵
Concomitant medication		X	Note changes daily until discharge, note on occurrence	X ⁵	X ⁵	X ⁵	X ⁵
AE and SAE evaluation				X ⁵	X ⁵	X ⁵	X ⁵
PROM							X
Endpoints assessment							
Endpoint assessment ⁸		X	X	X	X	X	X
Biobanking (level II)							
Serum, EDTA Plasma, Whole blood		X	Day 3, 8, 15, 22 (all ±1) or until discharge before D22				
Naso/oropharyngeal swab		X	Day 3, 8, 15 (all ±1) or until discharge before D15				
Add-on studies (level III)							
Biobanking, other material		X	Add-on sub protocols				
Radiology		X	Add-on sub protocols				
Organ function		X	Add-on sub protocols				
PROM		X	Add-on sub protocols				

Modular data capture according to level of commitment (level I, level II, level III). Assessments in level I are mandatory. Biobanking (level II) is necessary for virological end points. Add-on sub-studies (level III) will be developed in collaboration with participating sites, developing common standardised procedures for additional biobanking, radiology and organ function.

1. Refer to chapter 8 for details. Screening/baseline assessments should be performed prior to study drug administration.
2. See separate table 4.1 for WHO stage and allocation to EU-SolidAct Part A (moderate disease) or B (severe disease).
3. Standard of Care (SoC) details, including medication.

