3.1. Phase 3 Trial Objectives and Endpoints

In phase 3 confirmatory trials, the primary objectives and endpoints are described below. Secondary objectives and endpoints as listed below should be considered for all interventions studied within this platform. The final selection and any additional intervention-specific objectives or endpoints will be described in corresponding sub-protocols.

Table 3.1 Phase 3 objectives and corresponding endpoints

Objectives	Endpoints
Primary	
Part A, moderate disease	
The primary objective is to determine the effect of therapeutic interventions on occurrence of disease progression in hospitalized patients with moderate COVID-19	Occurrence of disease progression, defined as a progression of disease state from moderate (WHO score 4-5) to severe/critical (WHO score 6-9) or death (WHO score 10) within 14 days
Part B, severe disease	
The primary objective is to determine the effect of therapeutic interventions on occurrence of death in hospitalized patients with severe or critical COVID-19	Occurrence of death within 60 days
Secondary	
Secondary objectives are 1. to determine the effect of therapeutic interventions on other clinical endpoints	1.1 Occurrence of disease progression, defined as a progression of disease state from moderate (WHO score 4-5) to severe/critical/death (WHO score 6-10) or from severe/critical (WHO score 6-9) to death within 28 days 1.2 Time from randomization to sustained recovery, defined as being discharged from the index hospitalization, followed by being alive and at home for 14 consecutive days within 90 days

	
1.3 Time from randomization to first hospital discharge within 90 days
 
1.4 Disease state on a 5-point scale defined as:
 
 1. Mild (WHO score 1-3) or better, 2. Moderate (WHO score 4-5), 3. Severe (WHO score 6), 4. Critical (WHO score 7-9) or 5. Death at Day 15 and 29 
1.5 Time from randomization to recovery defined as no need for oxygen
 
1.6 SpO₂/FiO₂-ratio at day 3, 5 and 8

2. to determine the effect of therapeutic interventions on viral clearance	2. Viral clearance as assessed by SARS-CoV-2 PCR in oropharyngeal specimens during hospitalization

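### Part A progression is a cumulative, time-to-event endpoint, but the WHO score is registered only as status on scheduled days, with no worst score or onset date, so non-fatal events may be missed or misdated

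*Protocol*

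**What the plan says.** Table 3.1 (section 3.1) defines the Part A primary endpoint as progression from moderate disease to "severe/critical (WHO score 6-9) or death (WHO score 10) within 14 days". Secondary endpoint 1.1 extends this to 28 days. Section 9.3.2 analyses the primary endpoint by Kaplan-Meier, a stratified risk difference and a time-to-event regression, and section 9.3.3 applies the same methods to the 28-day endpoint.

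For data collection, section 8 (Assessment until discharge) states: "The following clinical data will be noted in the eCRF obtained on Days 3, 5, 8 (± 1 day), and thereafter weekly". The WHO score and oxygen therapy are on that list. The Schedule of Assessments (section 1.2) gives the same visits, "Day 3, 5, 8 (all ±1 day), then weekly (±3 d), or until discharge", and its footnote 7 says what the review is for: "Review WHO stage including mode of oxygen therapy for end point assessment (progression on WHO scale". Footnote 5 limits the later WHO reviews: "If still hospitalized. At discharge or early discontinuation, register WHO disease progression scale".

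For Days 15, 29 and 61, section 8 says: "If the patient has been discharged, the following information is gathered by phone or by reviewing the patient records". The items that follow are vital status, recovery status, readmission with date and reason, concomitant medication and adverse events. At the discharge visit, sites "register whether the patient is discharged to home, home care facilities, other hospitals or other institutions or locations". Footnote 8 of the schedule separately plans endpoint assessment after discharge by telephone, patient records, caretaker or relatives.

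**The concern.** A cumulative endpoint needs two facts per participant: whether score 6 was ever reached within the horizon, and when. The listed items give a snapshot on each visit day. A participant who starts high-flow oxygen on Day 9 and is back on nasal prongs by Day 13 can be scored 5 at every visit. An episode still present at the next visit is caught, but nothing in section 8 supplies its onset date.

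Two things are at stake. Missed events lower both arm rates and cost power. Capture also depends on how long a participant stays at score 6 or above, so an intervention that shortened episodes without preventing any would tend to look as if it reduced their occurrence. A larger sample does not remove that dependence, and an analysis plan cannot recover data that sites were not asked to record.

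**Working it through.** **1. Endpoint against collected items.** With Day 1 as baseline, 14 days ends at Day 15.

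- Before discharge: WHO score at Days 1, 3, 5, 8 (±1), 15 (±3), and at discharge or early discontinuation. No worst-since-last-contact score and no progression date.
- After discharge: the schedule's endpoint-assessment row and footnote 8 call for an assessment. Section 8's list has no WHO score and no oxygen support.
- Section 9.1 words the same endpoint as at day 15 in its text and at day 14 in its hypothesis table, so an explicit date matters.

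**2. Length of the gap (section 8 windows).** Nominal 15 − 8 = 7 days; shortest 12 − 9 = 3; longest 18 − 7 = 11. A visit on Days 12-14 leaves the end of the horizon unseen. A visit on Days 16-18 can show progression that began after it. Without an onset date the two cannot be separated.

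**3. The plan's own sample size (section 9.5.1, Table 9.2, scenario 1).** Inputs: 15% vs 10%, two-sided 5%, 90% power.

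- HR = ln(0.90)/ln(0.85) = 0.648, as stated.
- Freedman events = (1.960 + 1.282)² × [(1 + HR)/(1 − HR)]² = 230.8. Per arm: 230.8/(0.15 + 0.10) = 923.2, so 924, as stated.
- Schoenfeld events = 4 × (1.960 + 1.282)²/(ln HR)² = 223.8, so 224, as stated.

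**4. Effect of missed events on power.** Assumption: a share m of progressions is missed equally in both arms, and 15% vs 10% are the fully ascertained rates. Then a = 0.15(1 − m), b = 0.10(1 − m), h = ln(1 − b)/ln(1 − a), events d = 950(a + b), and power = Φ(√d × (1 − h)/(1 + h) − 1.96).

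| m | Rates | Events | Power at 950 per arm | N per arm for 90% |
|---|---|---|---|---|
| 0 | 15.0% vs 10.0% | 237.5 | 90.8% | 924 |
| 5% | 14.25% vs 9.5% | 225.6 | 89.1% | 979 |
| 10% | 13.5% vs 9.0% | 213.8 | 87.2% | 1041 |
| 20% | 12.0% vs 8.0% | 190.0 | 82.7% | 1187 |
| 30% | 10.5% vs 7.0% | 166.2 | 76.9% | 1374 |

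**5. Why episode length matters.** Assumptions: only the visit-day score counts, visits fall exactly on Days 3, 5, 8 and 15, onset is uniform over Days 1-15, and time at score 6 or above is exponential with mean D. For an interval of length L, the share of episodes over before the next visit is 1 − (D/L)(1 − e^(−L/D)). The intervals are 2, 2, 3 and 7 days.

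- D = 5: shares 0.176, 0.176, 0.248, 0.462. Weighted: (2×0.176 + 2×0.176 + 3×0.248 + 7×0.462)/14 = 33%. The Day 8-15 interval supplies 3.23 of the 4.68 in the numerator, about 69%.
- D = 3: 46%. D = 10: 20%.
- With early-weighted onset (exponential, mean 4 days), simulation gives 26%, 38% and 15% for D = 5, 3 and 10.

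These ignore deaths and every other capture route, so they are to be read as upper bounds. Their use is to show direction: the shorter the episode, the likelier the miss.

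**The case against.** The strongest reply is that the protocol has several other ways to see progression.

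- **After discharge.** The endpoint-assessment row covers Days 15, 29, 61 and 91 and does not carry footnote 5; footnote 8 says how it is done. A reader might infer that nothing is assessed after discharge, transfer or readmission. The documents do not support that. What stands is that section 8's list does not deliver what footnote 8 promises.
- **Transfer.** A WHO score is registered at discharge, and Table 8.1 scores support needed rather than received, so a participant already at 6 when moved can be scored. Section 3.3 also defines discharge as no longer needing hospitalization, which makes it unclear whether an acute transfer counts, although section 8 lists other hospitals as a destination. Deterioration after the move has no listed score.
- **Between visits.** Sections 6.3 and 8 provide for Part B screening soon after progression and re-randomization at any point. Adverse events are assessed daily, disease-related events go into daily eCRF sections, readmissions are reported as SAEs, and deaths within 24 hours. So it would be wrong to say that nothing covers the in-hospital gaps. But re-randomization is optional and needs an available Part B intervention. The Appendix 4 list includes severe ARDS but not the start of high-flow oxygen or NIV. No stated rule turns these reports into a dated score of 6.
- **Documents not shown.** The eCRF manual, the SAP or a Part A sub-protocol could contain such fields or rules. That is possible, but date derivation in an SAP still needs a recorded date.
- **Planning rates.** The 15% comes partly from rates observed in two earlier trials whose ascertainment is not described. If those already carried similar losses, the power cost in step 4 is overstated. This objection stands.

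**Conclusion.** The mismatch is real and lies in the protocol itself: a cumulative, dated endpoint is fed by undated snapshots, with a 7-day gap (up to 11) before the primary time point and a post-discharge list that does not match footnote 8. Non-fatal progression may be missed or misdated, more so for short episodes. Section 4.2 chose progression because death is much less frequent in moderate disease, so this is the component that matters most.

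The size is not known. The fall in power from about 91% to about 87-77% rests on an assumed 10-30% loss, equal in both arms, and on the planning rates being complete. A reader might go further and infer that a definite share of events is lost, or that the type I error is inflated by a particular amount because episodes differ in length between arms. The documents give no episode lengths, no capture rates and no arm difference, so only the direction of that risk can be stated.

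The scope is Part A phase 3 trials and the 28-day progression endpoint for participants entering with moderate disease. For severe entrants the 28-day endpoint is death. The baricitinib sub-protocol is a Part B trial with death as its primary endpoint. Neither is affected.

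**What to change.** At each scheduled assessment, at discharge or transfer, and at the Day 15 and Day 29 contacts, record from the medical record, including that of any receiving or readmitting hospital:

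1. the highest WHO score since the last contact;
2. the date score 6 or above was first reached, if it was.

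Look back to the exact 14- or 28-day horizon, whatever day the contact falls on. State in section 9.3 that this date defines the event for the primary and 28-day progression endpoints. Add the same items to section 8's post-discharge list so that it agrees with footnote 8. Once an onset date is recorded, the visit windows and footnote 5 can stay as they are.

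The cost is two eCRF fields, a wording change in section 8 and the schedule, and somewhat more record review, including record requests for transferred or readmitted participants. Sites already see inpatients daily for adverse events.
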